9.0 Vulnerable Populations*

If the research involves special populations that are considered vulnerable, describe the safeguards included to protect their rights and welfare.

NOTE: You should refer to the appropriate checklists, referenced below, to ensure you have provided adequate detail regarding safeguards and protections. You do not, however, need to provide these checklists to the IRB.

9.1 *For research that involves **pregnant women**, safeguards include:*

NOTE CHECKLIST: Pregnant Women (HRP-412)

Response:

N/A: This research does not involve pregnant women.

9.2 *For research that involves **neonates of uncertain viability or non-viable neonates**, safeguards include:*

NOTE CHECKLISTS: Non-Viable Neonates (HRP-413), or Neonates of Uncertain Viability (HRP-414)

Response:

N/A: This research does not involve non-viable neonates or neonates of uncertain viability.

9.3 *For research that involves **prisoners**, safeguards include:*

NOTE CHECKLIST: Prisoners (HRP-415)

Response:

N/A: This research does not involve prisoners.

9.4 *For research that involves **persons who have not attained the legal age for consent to treatments or procedures involved in the research (“children”)**, safeguards include:*

NOTE CHECKLIST: Children (HRP-416)

Response:

N/A: This research does not involve persons who have not attained the legal age for consent to treatments or procedures (“children”).

9.5 *For research that involves **cognitively impaired adults**, safeguards include:*

NOTE CHECKLIST: Cognitively Impaired Adults (HRP-417)

Response:

N/A: This research does not involve cognitively impaired adults.

9.6 *Consider if other specifically targeted populations such as students, employees of a specific firm, or educationally or economically disadvantaged persons are vulnerable. Provide information regarding their safeguards and protections, including safeguards to eliminate coercion or undue influence.*

Response: NA

10.0 Eligibility Screening*

10.1 Describe screening procedures for determining subjects' eligibility.

Screening refers to determining if prospective participants meet inclusion and exclusion criteria.

Include all relevant screening documents with your submission (e.g. screening protocol, script, questionnaire).

Response: All patients in NAVIGATE meet the inclusion criteria of first episode psychosis because it is a criteria for program entry. These patients are almost always on an antipsychotic medication. Co-investigator [name], who is the director of the NAVIGATE program, will determine from medical records whether patients meet criteria for age and antipsychotic medication. She will also determine whether the patient has a substance use disorder or an eating disorder on the basis of the medical records. [name] will determine if the patient and a family member involved in the treatment would be interested in the program. Interested patients and family members will be asked to sign a permission form for the research staff to contact them by phone. Research staff will contact the patient and family member, describe the program, determine their continued interest, and screen the family member with respect to residing with the patient, willingness to participate in the program activities. They will also screen the family member with respect to current substance use, ability to use technology, ability to weight themselves daily, and if female, whether they are currently pregnant or planning to be. Demographic factors including education will be assessed. If patients or family members did not complete high school, they will be told that there are written materials and they will need to complete a brief reading assessment at the first session.

N/A: There is no screening as part of this protocol.

Recruitment Methods

N/A: This is a records review only, and subjects will not be recruited. *NOTE: If you select this option, please make sure that all records review procedures and inclusion/exclusion screening are adequately described in other sections.*

10.2 Describe when, where, and how potential subjects will be recruited.

NOTE: Recruitment refers to how you are identifying potential participants and introducing them to the study. Include specific methods you will use (e.g. searching charts for specific ICD code numbers, Research Participant Groups, posted advertisements, etc.)

Response: Potential patients and parents in the NAVIGATE program will be identified by the director and clinical staff and will describe the availability of a weight management program designed to help patients maintain a healthy weight

or lose weight. If they are interested, the patient and family member will sign a permission form to provide contact information to the research staff.

10.3 Describe how you will protect the privacy interests of prospective subjects during the recruitment process.

NOTE: Privacy refers to an individual's right to control access to him or herself.

Response: Only patients who indicate an interest in participating will be contacted by the research assistant. All identifying information about participants and parents who are not eligible or who choose not to participate will be deleted.

10.4 Identify any materials that will be used to recruit subjects.

NOTE: Examples include scripts for telephone calls, in person announcements / presentations, email invitations.

 For advertisements, include the final copy of printed advertisements with your submission. When advertisements are taped for broadcast, attach the final audio/video tape. *NOTE: You may submit the wording of the advertisement prior to taping to ensure there will be no IRB-required revisions, provided the IRB also reviews and approves the final version.*

Response: NA

11.0 Procedures Involved*

11.1 Provide a description of **all research procedures or activities being performed and when they are performed once a subject is screened and determined to be eligible. Provide as much detail as possible.**

NOTE: This should serve as a blueprint for your study and include enough detail so that another investigator could pick up your protocol and replicate the research. For studies that have multiple or complex visits or procedures, consider the addition of a schedule of events table in in your response.

Response: Participants and a household family member will have a baseline session. In this session, they will be asked to sign the consent and assent forms. They will be given a brief reading test to ensure they can read at the 8th grade level. They will then complete the Behavioral Choice Questionnaire that assesses the reinforcing value of food. They will also complete questionnaires regarding time perspective, consideration of future consequences, and have their height and weight measured.

Following the baseline assessment, daily weights will be collected over a two month period, and then families will be randomized to staggered initiation of treatment in blocks of 4 families. A Bluetooth scale will be provided.

Families will receive a 12-week FBT adapted for first episode psychosis. This will be delivered in 12 weekly meetings with a trained case manager and two “eating plan” education sessions. Both the patient with psychosis and parents are targeted for eating and activity/exercise change to ensure a change in the shared family environment, which will also help weight control in both sets of participants, as well as medical issues that accompany obesity, including glycemic control, hypertension and hyperlipidemia. If parents are not overweight/obese, they will still target improved health behaviors. They will learn about GREEN, YELLOW, and RED foods (healthy vs. unhealthy foods), energy density, glycemic index of foods, reducing serving sizes, eating less, healthy lifestyle and programmed activity programs and recording their diets and activity. Weekly sessions will involve discussion of weight loss principles presented in modules in the weight control manual, and coaching parents and patients how to implement the Traffic Light Eating Plan and healthy lifestyle techniques. At each session, participants meet with staff and attend a brief problem solving session with their case manager where they will troubleshoot any expected or encountered issues with implementing the program. As part of treatment, participants will weigh themselves daily with a Bluetooth scale. Contingency management (\$1 per completed weighing) will be used to facilitate adherence to this weighing schedule.

An innovative aspect of this treatment is helping patients develop alternative reinforcements that do not involve food that can reduce the motivation to eat for the hedonic or reinforcing motivations. The first step is to identify alternative activities that have a higher reinforcement value than the patients’ favorite foods. First, participants will identify potential alternatives from the 139 behaviors on the Pleasant Activities List. The therapist then works with the patient to better specify the behavior, ensure its feasibility and describe the parameters of the behavior (e.g. duration). After the participant and case manager agree on a list of alternatives (at least 5), the participant will complete the Behavioral Choice Questionnaire that assesses the reinforcing value of that activity in comparison to food. The most reinforcing food to be used to assess behavioral substitutes will be chosen from a list of usual meals that can be obtained from home cooked, fast food or casual dining restaurants. These alternative reinforcements are used non-contingently by the patients/parents to provide highly desirable activities that compete with excessive food consumption.

At the end of treatment, the patient and family member will receive the same assessment battery that they completed for the baseline session. They will also provide information on the implementation of the diet, exercise, and alternative reinforcement procedures.

After an additional 2 months, the patient and family member will return for the final assessment using the same assessment battery, as well as the

implementation data. Families will be compensated for completing the assessment, sign their payment form, and be debriefed.

11.2 Describe what data will be collected.

NOTE: For studies with multiple data collection points or long-term follow up, consider the addition of a schedule or table in your response.

Response: The primary data collected will be daily weight, which will be taken with a Bluetooth scale that they will be given by the project. This data will be collected throughout the 2 month baseline, 3 month intervention, and 2 month follow up.

At the beginning of the baseline, and the end of treatment, and at the end of the follow-up patients and parents will complete a questionnaire including the Behavioral Choice Questionnaire, and scales regarding parenting, time perspective, and consideration of future consequences.

11.3 List any instruments or measurement tools used to collect data (e.g. questionnaire, interview guide, validated instrument, data collection form).

Include copies of these documents with your submission.

Response: Behavioral Choice Questionnaire, Consideration of Future Consequences Scale, Zimbardo Time Perspective Inventory, Demographic Form for Participant and Family Member

11.4 Describe any source records that will be used to collect data about subjects (e.g. school records, electronic medical records),.

Response: The identified patients' medical records at Erie County Medical Center (Meditech) will be accessed to confirm antipsychotic medications, antipsychotic medications start date and dose, changes in dose, and other changes in medication. Comorbid medical conditions and medications will also be recorded. The EMR may be accessed throughout the study to confirm any antipsychotic dosing changes and weight at clinic visits (if participant is non-compliant with daily weigh-ins). In addition, HDL, LDL, Triglycerides, Total cholesterol and AC1 information will be gathered from the records throughout the baseline, treatment, and follow-up periods.

11.5 Indicate whether or not *individual* subject results, such as results of investigational diagnostic tests, genetic tests, or incidental findings will be shared with subjects or others (e.g., the subject's primary care physician) and if so, describe how these will be shared.

Response: The participants will be aware of their test results because they will be weighing themselves daily.

11.6 Indicate whether or not study results will be shared with subjects or others, and if so, describe how these will be shared.

Response: Study results will be shared with the patients and their parents at the end of the follow-up. These will be shared with a letter and an invitation to contact one of the study team members ([name] or [name]) for any questions. The aggregate data will be presented at conferences and in publications and other presentations.

12.0 Study Timelines*

12.1 Describe the anticipated duration needed to enroll all study subjects.

Response: We expect to enroll all study subjects within 6 months.

12.2 Describe the duration of an individual subject's participation in the study. Include length of study visits, and overall study follow-up time.

Response: Participants will be involved in the study for a total of up to 9 months. They will have 3 in person assessments, and 12 weekly interventions via zoom or or in person. The assessments and the weekly interventions will take approximately 1 hour.

While we expect participation to be completed in 7 months (2 months baseline, 3 months treatment, 2 months follow-up), we are allowing extra time for the rescheduling of missed appointments, etc.

12.3 Describe the estimated duration for the investigators to complete this study (i.e. all data is collected and all analyses have been completed).

Response: We expect to be able to complete the analyses within 6 months of the final follow-up assessment.

13.0 Setting

13.1 Describe all facilities/sites where you will be conducting research procedures. Include a description of the security and privacy of the facilities (e.g. locked facility, limited access, privacy barriers). Facility, department, and type of room are relevant. Do not abbreviate facility names.

NOTE: Examples of acceptable response may be: "A classroom setting in the Department of Psychology with a computer with relevant survey administration software," "The angiogram suite at Buffalo General Medical Center, a fully accredited tertiary care institution within New York State with badge access," or, "Community Center meeting hall."

Response: The assessments and interventions will be conducted at the NAVIGATE clinic at Erie County Medical Center. Private offices are available for the assessments and interventions.

13.2 For research conducted outside of UB and its affiliates, describe:

- *Site-specific regulations or customs affecting the research*
- *Local scientific and ethical review structure*

NOTE: This question is referring to UB affiliated research taking place outside UB, i.e. research conducted in the community, school-based research, international research, etc. It is not referring to multi-site research. UB affiliated institutions include Kaleida Health, ECMC, and Roswell Park Cancer Institute.

Response:

N/A: This study is not conducted outside of UB or its affiliates.

14.0 Community-Based Participatory Research

14.1 Describe involvement of the community in the design and conduct of the research.

NOTE: Community-Based Participatory Research (CBPR) is a collaborative approach to research that equitably involves all partners in the research process and recognizes the unique strengths that each brings. CBPR begins with a research topic of importance to the community, has the aim of combining knowledge with action and achieving social change to improve health outcomes and eliminate health disparities.

Response:

N/A: This study does not utilize CBPR.

14.2 Describe the composition and involvement of a community advisory board.

Response:

N/A: This study does not have a community advisory board.

15.4 Describe your process to ensure that all persons assisting with the research are adequately informed about the protocol, the research procedures, and their duties and functions.

Response:

A project manual describe the processes and procedures will be developed for training purposes. [name] and [name] will train staff assisting in the assessment. The therapist who conducts the intervention has been conducting similar interventions in [name] research program for more than 10 years.

15.5 Describe any approvals that will be obtained prior to commencing the research (e.g., school, external site, funding agency, laboratory, radiation safety, or biosafety).

Response: Approval from ECMC will be required after IRB approval.

N/A: This study does not require any other approvals.

16.0 Provisions to Protect the Privacy Interests of Subjects

16.1 Describe how you will protect subjects' privacy interests during the course of this research.

NOTE: Privacy refers to an individual's right to control access to him or herself. Privacy applies to the person. Confidentiality refers to how data collected about individuals for the research will be protected by the researcher from release. Confidentiality applies to the data.

Examples of appropriate responses include: "participant only meets with a study coordinator in a classroom setting where no one can overhear", or "the participant is reminded that they are free to refuse to answer any questions that they do not feel comfortable answering."

Response: Study visits take place via telemedicine or in a private room. Subject's data is shared with research staff as needed.

16.2 Indicate how the research team is permitted to access any sources of information about the subjects.

*NOTE: Examples of appropriate responses include: school permission for review of records, consent of the subject, HIPAA waiver. This question **does apply** to records reviews.*

Response: Participants (patients, parents or household members) ages 18 and over will sign a consent form. For participants ages 14-17, parents will sign a parental permission form and adolescents will sign an assent form.

17.0 Data Management and Analysis*

17.1 Describe the data analysis plan, including any statistical procedures. This section applies to both quantitative and qualitative analysis.

Response: The project is a multiple baseline single case experimental design, with a 2 month baseline data collection. Families will then be randomized to staggered initiation of treatment in blocks of 4 families. We anticipate having 8 participating families at the

beginning of the project and would randomly assign them to start the baseline assessment between 1 and 9 weeks into the project, with the treatment then beginning between weeks 9 and 17. Treatment completion for this initial cohort would be between weeks 21 and 29, and the final follow-up would occur between weeks 29 and 37. Families entering NAVIGATE after the recruitment of the first cohort will be randomly assigned to start the baseline from 1 to 9 weeks after entry. This will provide a significant baseline (2 months) for all participants with different initial points for the study.

Analysis of the daily weights will involve discontinuous growth curve analysis using multi-level modeling (Singer and Willet, 2003). Separate models are developed for each participant which include the daily weights from the baseline (60 days), treatment (90 days) and follow-up (60 days) phases. Given the nature of the data, we would hypothesize significantly different slopes for the baseline vs treatment phases. We would also expect no significant differences between the slopes for the treatment phase and the follow-up phase. The primary analysis involves modeling each individual as a level one variable.

17.2 *If applicable, provide a power analysis.*

NOTE: This may not apply to certain types of studies, including chart/records reviews, survey studies, or observational studies. This question is asked to elicit whether the investigator has an adequate sample size to achieve the study objectives and justify a conclusion.

Response: NA

17.3 *Describe any procedures that will be used for quality control of collected data.*

Response: Data will be reviewed by trained and IRB approved study personnel.

18.0 **Confidentiality***

A. Confidentiality of Study Data

Describe the local procedures for maintenance of confidentiality of study data and any records that will be reviewed for data collection.

A

18.1 A. *Where and how will all data and records be stored? Include information about: password protection, encryption, physical controls, authorization of access, and separation of identifiers and data, as applicable. Include physical (e.g. paper) and electronic files.*

Response: Paper information (questionnaires, consent forms) will be transported by [name] to his ECMC office and stored in a locked filing cabinet. The master list linking participant identification and study ID will be kept in a separate

locked file in his office. Electronic data will be stored in a secure UB BOX folder. Drs. [name], [name], and [name] will have editor privileges, the research assistant will have read privileges of the de-identified master data file.

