5.0 Study Design*

5.1 *Describe and explain the study design (e.g. case-control, cross-sectional, ethnographic, experimental, interventional, longitudinal, observational).*

Response: This is a multiple baseline N of 1 design. Participants will chart their weight for two months prior to the initiation of a weight management program, and continue to chart their weight throughout the 3 month intervention and for 2 months following the intervention.

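### Sections 11.1 and 17.1 randomise different things, and under the detailed 17.1 schedule the per-participant slope comparison cannot separate treatment from slowing antipsychotic weight gain or time-in-study effects

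*Combined protocol and SAP*

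**What the plan says.** Two randomisations are described.

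- **Treatment start.** Section 11.1: "daily weights will be collected over a two month period, and then families will be randomized to staggered initiation of treatment". The second sentence of the 17.1 response agrees: "Families will then be randomized to staggered initiation of treatment in blocks of 4 families".
- **Baseline start.** The detailed schedule in 17.1 would take the first eight families and "randomly assign them to start the baseline assessment between 1 and 9 weeks into the project", with treatment following in weeks 9 to 17. Families who enter after "recruitment of the first cohort will be randomly assigned to start the baseline from 1 to 9 weeks after entry".

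Baseline length is fixed throughout. Section 5.1: "Participants will chart their weight for two months prior to the initiation of a weight management program". Section 11.2: "This data will be collected throughout the 2 month baseline, 3 month intervention, and 2 month follow up". Section 12.2 gives the same three durations, and the $210 payment cap at $1 a day equals 60 + 90 + 60 days.

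On analysis, 17.1 states: "Separate models are developed for each participant which include the daily weights from the baseline (60 days" for baseline, then 90 and 60 days for treatment and follow-up). The expectation is: "we would hypothesize significantly different slopes for the baseline vs treatment phases". The same paragraph also names multilevel modelling, and calls primary an analysis in which each individual enters at level one. It names no covariates.

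Section 4.1 reports that weight keeps rising over the first year on antipsychotics and then levels off. Section 11.4 collects the antipsychotic start date.

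**The concern.** Staff cannot carry out both randomisations, and the choice cannot be recovered once families have been assigned.

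The choice also decides what the stagger protects against. In a multiple-baseline design the protection comes from treatment starting at different points in otherwise comparable series. If only the calendar date of a fixed-length baseline varies, every series changes phase at the same day of weighing. Anything that evolves with day of weighing, or with time on drug within a person, then changes alongside treatment.

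The protocol's own background supplies one such process. In a patient whose drug-related gain is slowing, the later slope is lower than the earlier one with no treatment effect, which is the pattern 17.1 hopes to see. Weight is the primary endpoint and the programme's effect is part of the primary objective, so a misread slope change would bear on the main result.

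**Working it through.** **1. Reproduce the schedule (17.1).** Add 8, 12 and 8 weeks to the baseline start. Week 1 gives treatment at 9, completion at 21 and follow-up at 29. Week 9 gives 17, 29 and 37. These match the stated ranges. The lag from first weighing to treatment is 8 weeks for every family: day 57 counted in weeks, day 61 counted by the 60-day phase.

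**2. What the stagger identifies.** With a common lag, the treatment-slope term max(0, day − 60) is the same function of day of weighing in every family. For eight families, regressing it on person and day-of-weighing effects gives R² = 1.000, so it is not identifiable against a free common time-in-study effect. With calendar-day effects instead, R² = 0.946, so calendar events remain separable, but only in a model across families.

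**3. Size of the drug-time artefact, no treatment effect.** Assume W(t) = A(1 − exp(−t/τ)), t in weeks, with W(12) = 10.34 lb (olanzapine, 4.1). Assume also 90% or 95% of plateau at 52 weeks:

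- 90%: τ = 52/ln 10 = 22.6; A = 10.34/(1 − exp(−12/22.6)) = 25.1 lb.
- 95%: τ = 52/ln 20 = 17.4; A = 20.7 lb.
- Faster curve, also through 3.74 lb at 2 weeks (healthy participants, 4.1): τ = 5.0; A = 11.4 lb.

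Fit separate lines to days 0–59 and 60–149. Slope change in lb/week, by weeks on drug when weighing starts:

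| Weeks on drug | 90% | 95% | Faster |
|---|---|---|---|
| 0 | −0.35 | −0.43 | −0.92 |
| 26 | −0.11 | −0.10 | −0.005 |
| 52 | −0.035 | −0.02 | 0.00 |

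The change scales as exp(−weeks/τ). For example, −0.347 × exp(−26/22.6) = −0.11.

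**4. Against one participant's noise.** With independent daily noise the standard error of the slope change is 0.0594 × SD. At an assumed SD of 1.5 lb this is 0.089 lb/week, so −0.35 is 3.9 standard errors and −0.10 is 1.1. A separate simulation used autocorrelated noise (correlation 0.3–0.6, SD 1.5–2.5 lb, τ 90–180 days, 10.34 or 15.2 lb at 12 weeks). It found a falsely significant slope reduction in 19–100% of participants at drug start, 14–70% at 90 days, 5–34% at 180 days and 2–12% at one year. A straight-line null gave 3–5%.

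**5. Average over 12 patients.** Section 7.3 gives 40–45 existing patients and 10–15 new ones. New patients are therefore 10/55 = 18% to 15/55 = 27% of the pool, or 2–3 of 12. Take 2 new patients, treat admission as drug start, and start baseline 1–9 weeks later. Programme size over admission rate gives 40/3 = 13.3 to 45/2 = 22.5 months.

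- If all existing patients have already been on drug 13.3–22.5 months, their mean change is −0.005 to −0.010 and the new patients' is −0.28 to −0.33. Then (10 × −0.010 + 2 × −0.28)/12 and (10 × −0.005 + 2 × −0.33)/12 both come to about −0.06 lb/week.
- If existing patients are spread evenly from zero up to 13.3 or 22.5 months, the mean is −0.10 to −0.13.

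For scale, the largest first-episode trial in 4.1 implies (15.2 − 9.0)/12 = 0.52 lb/week. These artefacts are about 12% (0.06/0.52) to 25% (0.13/0.52) of it.

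**6. Can a pooled model remove it?** Use 12 patients, person intercepts and slopes, and treatment and follow-up level and slope terms: 24 + 4 columns.

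- A linear drug-time term makes 29 columns of rank 28. Time on drug is a person constant plus day of weighing, so it is aliased.
- log(1 + weeks since drug start) gives 29 columns of rank 29.
- In noise-free fits with the log term, the −0.06 case falls to between 0.00 and +0.02. The −0.10 to −0.13 cases fall to between −0.03 and 0.00. The faster curve leaves 0.00 to +0.02.
- Adding a quadratic in day of weighing is hazardous. A real −0.52 lb/week effect that ramps up over 4 or 6 weeks is then estimated at about −0.26 or −0.07, against about −0.47 or −0.43 without the quadratic.

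**The case against.** The strongest reply is that this is a pilot of acceptability and potential value, that 2.2 predicts actual weight loss, and that many first-cohort patients may be past the steep part of the curve. Much of that stands. A plateau flattens a gain and cannot turn it into a loss, so observed loss would not be explained this way. After about a year on drug the artefact is close to nil. But the test written in 17.1 is a difference in slopes, which a flattening gain does satisfy.

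A second reply is that 17.1 names multilevel modelling, so a pooled analysis may be intended. It may, but the same paragraph specifies separate models per participant. What remains is that the primary inference is unclear. Nor does 17.1 rule out a drug-time term; it is silent.

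A reader might infer more than the documents support:

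- *That the stagger is worthless.* It still guards against calendar or clinic-wide events, provided the analysis compares families.
- *That reactivity to daily weighing flatters the programme.* The documents give neither its size nor its shape. An early drop that rebounds would imitate benefit; a loss that builds and then holds would hide it.
- *That baseline length must be varied.* That is one possible design, but it would not repair tests done one participant at a time.

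**Conclusion.** The contradiction over what is randomised is on the page and needs resolving. If the detailed schedule is the one followed, the fixed lag and the resulting confounding with time in study follow by arithmetic, without modelling assumptions.

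The size of the drug-time artefact is conditional. It rests on the assumed exponential plateau, the olanzapine figure and time on drug, which the documents do not report. It is material for patients enrolled in their first months of treatment and negligible after about a year. The documents do not support saying that any slope change seen in this study would be an artefact. They support saying that the planned per-participant comparison cannot show that it is not.

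**What to change.** 1. **Before the first family is assigned**, reconcile 11.1, the second sentence of the 17.1 response and the 17.1 schedule so that one quantity is randomised.
2. **Before any weights are analysed**, add to 17.1 a pooled multilevel model of the patients' weights. Include person intercepts and slopes, phase level and slope terms (follow-up included), and a curved term in time since antipsychotic start such as log(1 + weeks), from the date already collected under 11.4. Keep the per-participant models as description. Use a quadratic in day of weighing as a sensitivity analysis only.
3. **If the fixed 60-day baseline is kept**, state that a slope change will not by itself be read as a treatment effect, because time-in-study effects are not controlled by design.

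The cost is a short amendment to 11.1 and 17.1 and some analyst time; visits and payments do not change. Precision falls somewhat. In the step 6 model with independent noise, the standard error of the treatment slope rises from 0.0172 × SD to 0.018–0.019 × SD, and the loss is greater if daily weights are autocorrelated. The correction also relies on the assumed curve. In simulated no-effect trials with 0 to 4 new admissions, baseline and treatment phases only, the log term cut false rejection from 13–99% to 4–27%, so it reduces the problem without removing it.
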